3.2 Analysis Populations

3.2.1 Immune Response

The immune response population will be defined as subjects who receive 3 infusions of sipuleucel-T and 10 or more weeks of enzalutamide. Analysis of immune response endpoints, including the primary endpoint, will be performed using this population. This population will also be used to perform supplementary analyses of nonimmune response efficacy endpoints.

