3.2.3 Safety

The safety population is defined as all randomized subjects who undergo at least one leukapheresis procedure or receive at least 1 dose of enzalutamide. All immune response variables and safety variables will be analyzed and summarized based on this analysis set. Immune response data and safety data for all subjects in the safety population will be included in the data listings. All the subjects in the safety population will be analyzed according to the treatment actually received.

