4.1 Product Characterization

Product parameters to be summarized are: CD54 upregulation, CD54⁺ cell count, and TNC count. Product parameters will be summarized descriptively (n, mean [geometric mean], standard error, median, minimum, and maximum) by Infusion (1, 2, and 3) and cumulative (summed across infusions). Cumulative product parameters will be compared between both arms using a Wilcoxon test based on the immune response population. Cumulative CD54 upregulation is the primary endpoint for the study.

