5 TABLES, LISTINGS, AND FIGURES

The content and format of all tables, listings, and figures will be specified in a separate report plan prior to final database lock of the trial.

The tables, listings, and figures specified below are intended to be a representation of the content that will be included in the clinical study report. It should be noted that the final outputs included in the actual clinical study report may not necessarily be an exact match of the content specified below.

Proposed tables. Title names and numbering subject to change.

Number	Title
14.1.1	Summary of Subject Disposition
14.1.2	Summary of Eligibility Criteria Not Met
14.1.3	Summary of Eligibility Deviations
14.1.4	Summary of All Protocol Deviations
14.1.5.1	Summary of Demographics and Baseline Characteristics – Intent-to-Treat Subjects
14.1.5.2	Summary of Demographics and Baseline Characteristics – Subjects Receiving 3 Infusions of Sipuleucel-T
14.1.6	Summary of Baseline Cerebrovascular Event (CVE) Risk Factors
14.2.1	Summary of Leukaphereses and Product Infusions
14.2.2	Summary of Time Interval (Days) Between Infusions
14.2.3	Summary of the Duration of Infusions (Minutes)
14.2.4	Summary of Subjects Undergoing > 1 Leukapheresis in Order to Receive a Given Infusion
14.2.5	Summary of Number of Leukaphereses by Infusion
14.2.6.1	Duration of Exposure to Enzalutamide
14.2.6.2	Summary of Reasons for Stopping Enzalutamide
14.2.6.3	Duration of Exposure to Non-Protocol Enzalutamide
14.2.6.4	Summary of Reasons for Stopping Non-Protocol Enzalutamide
14.2.7.1	Summary of CD54 Upregulation by Infusion Number for Subjects Receiving At Least 1 Infusion of Sipuleucel-T
14.2.7.2	Summary of CD54 Upregulation by Infusion Number for Subjects Receiving 3 Infusions of Sipuleucel-T
14.2.8.1	Summary of CD54 ⁺ Counts by Infusion Number for Subjects Receiving At Least 1 Infusion of Sipuleucel-T
14.2.8.2	Summary of CD54 ⁺ Counts by Infusion Number for Subjects Receiving 3 Infusions of Sipuleucel-T
14.2.9.1	Summary of TNC Counts by Infusion Number for Subjects Receiving At Least 1 Infusion of Sipuleucel-T
14.2.9.2	Summary of TNC Counts by Infusion Number for Subjects Receiving 3 Infusions of Sipuleucel-T
14.2.10.1	Analysis of ELISPOT Counts (3 x 10 ⁵ per PBMC) for Subjects Receiving At Least 1 Infusion of Sipuleucel-T
14.2.10.2	Estimation of ELISPOT Treatment and Visit Effects for Subjects Receiving At Least 1 Infusion of Sipuleucel-T

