14.2.10.3	Analysis of ELISPOT Counts (3 x 10 ⁵ per PBMC) for Subjects Receiving 3 Infusions of Sipuleucel-T
14.2.10.4	Estimation of Treatment and Visit Effects for ELISPOT Data for Subjects Receiving 3 Infusions of Sipuleucel-T

14.2.10.5	ELISPOT Responder Analysis for Subjects Receiving At Least 1 Infusion of Sipuleucel-T
14.2.10.6	ELISPOT Responder Analysis for Subjects Receiving 3 Infusions of Sipuleucel-T
14.2.11.1	Analysis of ELISA Antibody Titers for Subjects Receiving At Least 1 Infusion of Sipuleucel-T
14.2.11.2	Estimation of Treatment and Visit Effects for ELISA Antibody Titer Data for Subjects Receiving at Least 1 Infusion of Sipuleucel-T
14.2.11.3	Analysis of ELISA Antibody Titers for Subjects Receiving 3 Infusions of Sipuleucel-T
14.2.11.4	Estimation of Treatment and Visit Effects for ELISA Antibody Titer Data for Subjects Receiving 3 Infusions of Sipuleucel-T
14.2.11.5	ELISA Antibody Titer Responder Analysis for Subjects Receiving At Least 3 Infusions of Sipuleucel-T
14.2.11.6	ELISA Antibody Titer Responder Analysis for Subjects Receiving 3 Infusions of Sipuleucel-T
14.2.12.1	Analysis of Cellular Proliferation for Subjects Receiving At Least 1 Infusion of Sipuleucel-T
14.2.12.2	Estimation of Treatment and Visit Effects for Cellular Proliferation Data for Subjects Receiving At Least 1 Infusion of Sipuleucel-T
14.2.12.3	Analysis of Cellular Proliferation for Subjects Receiving 3 Infusions of Sipuleucel-T
14.2.12.4	Estimation of Treatment and Visit Effects for Cellular Proliferation Data for Subjects Receiving 3 Infusions of Sipuleucel-T
14.2.12.5	Cellular Proliferation Responder Analysis for Subjects Receiving At Least 1 Infusion of Sipuleucel-T
14.2.12.6	Cellular Proliferation Responder Analysis for Subjects Receiving 3 Infusions of Sipuleucel-T
14.2.13.1	Analysis of AIM-V Cytokine Data for Subjects Receiving At Least 1 Infusion of Sipuleucel-T
14.2.13.2	Estimation of Treatment and Visit Effects for AIM-V Cytokine Data for Subjects Receiving At Least 1 Infusion of Sipuleucel-T
14.2.13.3	Analysis of AIM-V Cytokine Data for Subjects Receiving 3 Infusions of Sipuleucel-T
14.2.13.4	Estimation of Treatment and Visit Effects for AIM-V Cytokine Data for Subjects Receiving 3 Infusions of Sipuleucel-T
14.2.14.1	Analysis of Serum Cytokine Data for Subjects Receiving At Least 1 Infusion of Sipuleucel-T
14.2.14.2	Estimation of Treatment and Visit Effects for Serum Cytokine Data for Subjects Receiving At Least 1 Infusion of Sipuleucel-T

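### The SAP assigns the immune endpoints to conflicting analysis sets, and its 10-week enzalutamide rule filters the two arms at different times, chiefly affecting cumulative CD54 and immune visits up to week 14

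*SAP*

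**What the plan says.** SAP 3.2.1 (and protocol 8.3) defines the set for the immune endpoints, including the primary endpoint: "The immune response population will be defined as subjects who receive 3 infusions of sipuleucel-T and 10 or more weeks of enzalutamide". The same set serves for supplementary analyses of the non-immune efficacy endpoints.

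SAP 3.2.3 defines the safety set as randomised subjects with at least one leukapheresis or one enzalutamide dose, analysed by treatment received, and adds: "All immune response variables and safety variables will be analyzed and summarized based on this analysis set".

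The table titles in SAP section 5 follow neither. For proliferation they are "Analysis of Cellular Proliferation for Subjects Receiving At Least 1 Infusion of Sipuleucel-T" (14.2.12.1) and "Analysis of Cellular Proliferation for Subjects Receiving 3 Infusions of Sipuleucel-T" (14.2.12.3). ELISPOT, ELISA and cytokine tables follow the same pattern.

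SAP 4.1 applies the 3.2.1 set to the product data: "Cumulative product parameters will be compared between both arms using a Wilcoxon test based on the immune response population". It goes on: "Cumulative CD54 upregulation is the primary endpoint for the study". SAP 2.1 makes PA2024-specific T cell proliferation the primary objective.

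SAP 3.1 first planned 50 per arm to obtain 43, allowing for drop-out and for subjects who miss the 3-infusion or 10-week criterion. After enrolment was cut, it gives about 70% power with 25 per arm and mentions no allowance. In the event 25 and 27 were enrolled. SAP section 4 makes all tests exploratory.

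**The concern.** Two sections of the SAP name different sets for the same endpoints, so a programmer cannot tell which result is the main one. The trial is open-label and SAP 4.7.1 allows periodic immune summaries, so that choice should be fixed and documented.

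The 10-week rule also depends on what happens after randomisation, and enzalutamide starts at different times in the two arms. A sequential subject must stay on study much longer to be counted. The contrast is then not between the groups as randomised. If early stoppers respond differently from the rest, the arm ratio is distorted.

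The rule has least purpose for cumulative CD54. Those data are complete at the third infusion, before sequential subjects have started enzalutamide.

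**Working it through.** **1. The plan's power.** Inputs from SAP 3.1 and protocol 8.1: 2-fold ratio, coefficient of variation 1.25, two-sided 0.05. Log-scale SD = sqrt(ln(1 + 1.25²)) = 0.970; difference = ln 2 = 0.693. A two-sample t calculation gives:

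- 43 v 43: 90.6% (stated: about 90%)
- 25 v 25: 69.7% (stated: about 70%)
- 25 v 27, no exclusions: 71.4%
- 14% loss (1 − 43/50) from 25 and 27, leaving 21.5 and 23.2: 64.6%

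Both stated figures reproduce. The second has no room for exclusions.

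**2. When the rule is met, counted from infusion 1.**

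- Concurrent: enzalutamide starts 14 days before leukapheresis 1, and infusion follows about 3 days later, so the start is day −17. Then −17 + 70 = day 53, week 7.6.
- Concurrent at the 42-day limit (protocol Table 1, footnote c): start day −45; −45 + 70 = day 25, week 3.6. The third infusion, at about week 4, then becomes the limit.
- Sequential: start about week 10; 10 + 10 = week 20.

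The nominal gap is 20 − 7.6 = 12.4 weeks. Five of the nine scheduled post-baseline samples precede week 20: preleukapheresis 2 and 3, and weeks 6, 10 and 14.

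**3. Which visits are affected.** Under protocol 4.3.3 and 4.5, progression or withdrawal from treatment sends a subject in either arm to a post-treatment visit and long-term follow-up. Table 1 has no immune samples in long-term follow-up. A concurrent subject who stops this way at week 15 therefore contributes only samples taken before then. From week 20 both arms' scheduled samples come from subjects still on study.

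**4. Size, under stated assumptions.** The documents give no loss rate. Take the plan's 14% overall and a constant weekly rate h from infusion 1, solved from

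[25(1 − e^(−7.57h)) + 27(1 − e^(−20h))]/52 = 0.14, so h = 1.092% per week.

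Exclusions are then 7.9% concurrent and 19.6% sequential. At visit week v the gap is e^(−h·max(v, 7.57)) − e^(−h·max(v, 20)):

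| Visit | Gap (points) |
|---|---|
| Preleukapheresis 2 and 3, week 6 | 11.7 each |
| Week 10 | 0.8966 − 0.8038 = 9.3 |
| Week 14 | 0.8582 − 0.8038 = 5.4 |
| Weeks 20, 26, 40, 52 | 0 |

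Mean over nine visits: (3 × 11.7 + 9.3 + 5.4)/9 = 5.5 points.

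Shift in the ratio = exp(deficit × gap) − 1, with the deficit of excluded subjects assumed to be 0.5 to 1 SD (0.485 to 0.970):

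- Earliest visits: exp(0.970 × 0.117) − 1 = 12.0% at 1 SD; 5.8% at 0.5 SD.
- Averaged: exp(0.970 × 0.0553) − 1 = 5.5% at 1 SD; 2.7% at 0.5 SD.
- Counting loss from the first study procedure instead (10 v 20.43 weeks, h = 0.987%): 4.4-9.0% at the earliest visits and 2.2-4.4% averaged.
- If half the loss follows enzalutamide exposure, equal in both arms: 2.2-6.0% at the earliest visits and 1.1-2.8% averaged, over both clocks.

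The false-positive rate at the visit-averaged shift is 5.0-5.4% (noncentral t, remaining sample sizes, single-visit standard error). Averaging imperfectly correlated visits would shrink that standard error and raise the rate somewhat.

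**5. Cumulative CD54.** Data are complete at about week 4. Sequential subjects can still be removed for 20 − 4 = 16 weeks; concurrent subjects for 7.57 − 4 = 3.57 weeks. No CD54 variance is given, so no ratio shift is computed.

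**6. Supplementary survival and PSA.** Sequential members must survive and stay on treatment longer before they qualify: 12.4 weeks longer counted from infusion 1, or 20.43 − 10 = 10.4 weeks longer counted from the first study procedure.

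**The case against.** The best defence is that the 10-week set is in the protocol, that every test is exploratory, and that the effect is small. At 14% loss the 95% interval for the ratio is about ×/÷1.8 (exp(2.02 × 0.970 × sqrt(1/21.5 + 1/23.2))), far wider than the shift. The loss model probably overstates early calendar-time loss. For subjects without a PSA decline, PSA progression counts only after 12 weeks of enzalutamide (protocol 4.5, SAP 4.3), which is past the milestone in either arm. The plan's 14% also includes subjects without three infusions, a failure common to both arms. All of this stands and lowers the estimate.

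A reader might infer that the whole contrast is shifted by up to 12%, with a matching loss of power in one direction. The documents do not support this: that figure belongs to the earliest visits, and the gap is about nil from week 20. Two qualifications remain. A mixed model could carry part of the early gap forward. Under protocol 4.3.2, a subject who stops only enzalutamide after 10 weeks and three infusions continues to be sampled.

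A reader might also count four competing populations. The firm conflict is between 3.2.1 and 3.2.3. SAP section 5 calls its titles provisional and defers content to a separate report plan. The at-least-1 against 3-infusion pairing may simply be sensitivity analysis.

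Any set requiring an infusion is also selected after randomisation. In the concurrent arm the first infusion follows an enzalutamide run-in. That too stands, and is a cost of the fix.

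**Conclusion.** The conflict between SAP 3.2.1 and 3.2.3 is certain, as is the absence of the 10-week rule from every table title. The unequal timing (about week 7.6 v week 20) follows from the nominal schedule with uninterrupted dosing.

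The resulting bias is conditional and modest. With 14% loss and excluded subjects 0.5 to 1 SD lower, it is about 4-12% at the earliest visits and about 2-5.5% averaged if all loss follows calendar time, or about 1-3% averaged if half does. Nothing in the documents shows that excluded subjects respond less, so which arm is favoured is unknown.

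Cumulative CD54 is the clearest case, because the rule acts wholly after the data are complete. The 70% power is arithmetically right for 25 evaluable per arm, but it omits the section's own allowance; with it, power is about 65%. Because the tests are exploratory, this affects how an estimate is read and which result is reported, not a confirmatory claim.

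**What to change.** 1. **Peripheral immune endpoints.** Remove immune response variables from the analysis sentence in SAP 3.2.3. Name one main set: randomised subjects with at least one infusion and at least one post-baseline sample, analysed as randomised, using the planned at-least-1-infusion tables. Report the protocol 8.3 set alongside, with exclusions by arm and reason. Record the change and which immune summaries had already been seen.
2. **Product data.** For cumulative CD54 upregulation, CD54+ count and TNC count, drop the 10-week criterion and use randomised subjects with three infusions. Planned tables such as "Summary of CD54 Upregulation by Infusion Number for Subjects Receiving 3 Infusions of Sipuleucel-T" (14.2.7.2) already use that set, although the cumulative comparison needs its own entry. Protocol 8.5.6.1 also uses the immune response set here, so disclose the departure. Reconcile the primary-endpoint statement in SAP 4.1 with SAP 2.1.
3. **Supplementary survival and PSA.** Drop the randomisation-timed analyses in the 10-week set, or landmark them at a common time.
4. **Power.** Restate as about 65% at 14% non-evaluable, or from the actual evaluable counts.

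A tipping-point analysis for samples missing after early stopping is optional. Title 14.2.11.5, "ELISA Antibody Titer Responder Analysis for Subjects Receiving At Least 3 Infusions of Sipuleucel-T", looks like a slip for at least 1 and can be corrected at the same time.

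The cost is SAP editing and a few added outputs, with no new data. The downsides are a late, disclosed departure from the protocol set in an open-label trial, some partly treated subjects in the main analysis, and a main set still conditioned on reaching infusion 1.

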3.2.2 Intent-to-treat (ITT)

The ITT population is defined as all randomized subjects regardless of whether they received treatment. Analysis of nonimmune response efficacy endpoints will be performed using this analysis population. Efficacy data for all randomized subjects will be included in the data listings. All the subjects in the ITT population will be analyzed according to the treatment that they are randomized to receive.

3.2.3 Safety

The safety population is defined as all randomized subjects who undergo at least one leukapheresis procedure or receive at least 1 dose of enzalutamide. All immune response variables and safety variables will be analyzed and summarized based on this analysis set. Immune response data and safety data for all subjects in the safety population will be included in the data listings. All the subjects in the safety population will be analyzed according to the treatment actually received.

3.3 Missing Data

Missing data will not be imputed for any variables except in the case of time-to-event variables. The rules for imputing missing event or censor dates are defined below (section 3.4).

3.4 Data Rules

- *Study Day* = [(visit date) – (date of first infusion [Day 0])]. If the infusion does not occur, Day 0 will be the date of the first leukapheresis, unless it fails, in which case, Day 0 will be the date of registration.
- *Baseline*: baseline is defined as the value closest to but prior to the randomization data.
- *Change from baseline*: change from baseline is the post-baseline value minus the baseline value.
- *Percent change from baseline*: percent change from baseline is calculated as $100 \times (\text{post-baseline value} - \text{baseline value}) / \text{baseline value}$. If the baseline or post-baseline value is missing, then the change from baseline and percent change are set to missing. If the baseline value is zero and the post-baseline is non-zero, then the percent change from baseline is set to missing. If the baseline value is zero and the post-baseline value is also 0, then the percent change from baseline is set to 0.
- *Partial Dates*: Dates missing the day, month and year and the day and month will not be imputed. However, if the month and year are present, the day may be set to the 15th of the month or to a date consistent with a more conservative approach to the analysis of the data point.
- *Missing event or censor date*: If the date of an event or the date of censoring is missing for a time-to-event variable, the last known study date will be used. Subjects who prematurely discontinue from the study before having the event will be censored at their last known alive date.

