After 52 weeks of enzalutamide treatment provided by Dendreon, subjects in either treatment arm may continue to receive enzalutamide obtained from other sources at the discretion of their treating physician. Dendreon cannot provide enzalutamide beyond the protocol-specified duration of 52 weeks.

All subjects will receive a total of 52 weeks of enzalutamide. The active phase will begin at registration and continue through the post-treatment visit (30 to 37 days following the last study

treatment). The long term follow-up (LTFU) phase will begin after the post-treatment visit and will continue until the subject's death or until Dendreon terminates the study.

All immune monitoring (IM) endpoints will be collected from all subjects who receive at least one infusion. Cellular and serological peripheral immune responses will be assessed for subjects in both arms. In both arms, IM blood samples will be collected at baseline (screening); pre-leukapheresis 2 and 3; and weeks 6, 10, 14, 20, 26, 40, and 52, with the timing of visits based on the date of the first sipuleucel-T infusion (Day 0).

During the Active phase, safety assessments in both arms will include AE monitoring, laboratory tests (complete blood count (CBC) collection serum chemistries, and liver function tests [LTFs]), vital signs, Eastern Cooperative Oncology Group (ECOG) performance status, anticancer therapies, first opioid use for cancer-related pain, PSA monitoring, and physical examinations.

During the LTFU phase, safety (treatment-related AEs, cerebrovascular events, and seizures), survival status, PSA, ECOG performance status, first opioid use for cancer-related pain (if applicable), and anticancer therapies will be assessed every 3 months until the subject's death or until Dendreon terminates the study.

Sponsor's decision to terminate the study: During the first quarter of 2017, a decision was made to terminate the study during 2017 after at least 3 years of follow-up data was collected on all subjects participating in the study and still being followed. The end of follow-up period was defined as 3 years after the date that the last enrolled subject received the last infusion of sipuleucel-T.

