4.6.9 Anti-Cancer Interventions and Cancer-Related Opioid Use

All anticancer therapies received prior to screening and through the end of the LTFU phase were collected. Anticancer therapies included, but were not limited to, radiation, chemotherapy, hormone therapy, investigational cancer therapies, all other systemic therapies, and surgery. Each subject's first cancer-related opioid use will be collected and is defined as an opioid used for cancer-related pain that is of at least 2 consecutive days in duration.

The time to next anticancer intervention will be summarized by treatment group and is defined as the time from randomization to the first anticancer intervention as described above. Subjects who do not received any anti-cancer therapies will be censored at the last available contact date. A Cox regression model with treatment arm as the independent variable and stratified by screening PSA levels and screening lactate dehydrogenase will be used to compare the treatment arms with respect to time to first anti-cancer therapy. A similar summary will be produced for the time to first chemotherapy post randomization and time to first cancer-related opioid use.

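### SAP 3.4 places a non-fatal event with a missing date at the last known study date, which can record it 2 to 3 years late and never early

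*SAP*

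**What the plan says.** SAP 3.3 sets the scope of imputation: "Missing data will not be imputed for any variables except in the case of time-to-event variables". It refers to 3.4 for the rules. SAP 3.4 then has two bullets that matter here.

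- **Partial dates.** "Dates missing the day, month and year and the day and month will not be imputed". A known month is used: "if the month and year are present, the day may be set to the 15th of the month", or a more cautious date may be chosen.
- **Missing event or censor date.** If the date of an event or of censoring "is missing for a time-to-event variable, the last known study date will be used".

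Neither document defines the last known study date. Neither has a rule that bounds an incomplete event date by the known year, by the visit that reported the event, or by the visit before it.

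The endpoints most exposed are in SAP 4.6.9. Time to next anticancer intervention is "the time from randomization to the first anticancer intervention as described above", and the SAP adds: "A similar summary will be produced for the time to first chemotherapy post randomization and time to first cancer-related opioid use".

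On length of follow-up, SAP 1 says that the study would end "after at least 3 years of follow-up data was collected on all subjects participating in the study and still being followed", and: "The end of follow-up period was defined as 3 years after the date that the last enrolled subject received the last infusion of sipuleucel-T". Contact in long-term follow-up is every 3 months until death or study termination.

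**The concern.** A missing censoring date and a missing event date are different problems. For a subject without the event, the last known date is the natural censoring time. For a subject known to have had a non-fatal event, it is about the latest time the event could have happened, because contact continues after the event. The rule therefore cannot average out: each affected time is too long or, at best, right.

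At stake are the Kaplan-Meier curves and medians for next anticancer intervention, first chemotherapy and first opioid use. A relocated event keeps the curve too high over the interval it skips, then drops it in the tail, where few subjects remain at risk. There is also a possible knock-on effect. SAP 4 allows efficacy observations after a next anticancer intervention to be censored at the date of that intervention. An opioid start that truly came before the new therapy but was moved past it could then be lost as an event.

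Deaths are not part of the point, since the last known study date would not normally fall after the death. PSA progression and ECOG decline rest on dated assessments and are much less exposed.

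**Working it through.** The plan gives no figure for the effect of this rule, so there is none to reproduce. The check is a reading of the rules followed by date arithmetic.

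**1. Which dates reach the rule (SAP 3.3 and 3.4)**

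| What is known of the event date | Partial-date bullet | Result |
|---|---|---|
| Month and year | Day 15, or a more cautious date | Under the default, stays in the known month |
| Nothing | Not imputed | Missing-date bullet applies: last known study date |
| Year only | Not imputed | Not stated; appears to fall to the missing-date bullet |

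The second row is explicit, although the two bullets conflict on their face (not imputed, against a date being used). SAP 3.3 resolves the conflict by making time-to-event variables the exception. The third row is an inference. The other reading leaves a known event with no analysis time, and does not use the known year either.

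**2. Size of the delay**

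Delay = last known study date − true event date. The minimum follow-up for subjects still followed is 3 years (SAP 1). Earlier enrollees have more, so 42 months is added as an illustration.

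| True event | Recorded at month 36 | Recorded at month 42 |
|---|---|---|
| Month 6 | 30 months (2.5 years) late | 36 months (3.0 years) late |
| Month 12 | 24 months (2.0 years) late | 30 months (2.5 years) late |
| Month 24 | 12 months (1.0 year) late | 18 months (1.5 years) late |

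**3. Year-only illustration, if the inference in step 1 is right**

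Assumed dates: randomized 1 December 2013, event known only to be in 2014, last study date 1 March 2017. These fit the SAP's calendar (enrolment stopped by notice in February 2014, termination in 2017).

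- Recorded day: (1 March 2017 − 1 December 2013) + 1 = 1187.
- True day: between 32 (1 January 2014) and 396 (31 December 2014).
- Delay: 1187 − 396 = 791 days (2.2 years) to 1187 − 32 = 1155 days (3.2 years).

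The event would be analysed in 2017 although it is known to have happened in 2014.

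**4. Effect on a curve**

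SAP 3.1 gives 25 and 27 subjects. Before censoring, one event is worth 1/25 = 4.0 or 1/27 = 3.7 percentage points. Two are worth 8.0 or 7.4 points, and three 12.0 or 11.1. The curve is too high by that amount between the true and assigned dates.

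**5. Illustrative simulation**

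All settings except the arm sizes are assumptions: 25 against 27 subjects, exponential times, true hazard ratio 1, true median 12 or 18 months, last study date at 36 to 40 months, 500 runs per setting.

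| Median | Dates missing, concurrent / sequential | 12-month event-free, concurrent: true → under rule | Hazard ratio: true dates → under rule |
|---|---|---|---|
| 12 | 10% / 10% | 49.5% → 54.5% | 1.00 → 1.00 |
| 12 | 20% / 20% | 49.6% → 59.8% | 1.00 → 1.00 |
| 18 | 10% / 10% | 63.6% → 67.2% | 0.99 → 0.99 |
| 18 | 20% / 20% | 63.7% → 71.0% | 0.97 → 0.97 |
| 12 | 10% / 0% | 49.0% → 54.3% | 1.02 → 0.85 |
| 12 | 20% / 0% | 49.6% → 59.7% | 1.02 → 0.72 |
| 18 | 10% / 0% | 62.6% → 66.1% | 1.01 → 0.90 |
| 18 | 20% / 0% | 62.2% → 69.9% | 1.04 → 0.83 |

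The mean delay of an affected event was 23 to 26 months, and 81% to 87% of affected events moved by more than a year. With equal missingness the curves shift but the hazard ratio does not. It moves only when missingness differs between arms.

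**6. Error under a bounded rule**

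Long-term follow-up contacts are every 3 months, ± 2 weeks (Protocol Table 1). If consecutive contacts are made, the widest gap is about 3 months + 2 × 2 weeks, or about 4 months. The midpoint is then off by about 2 months at most. For a year-only date with no better bound, mid-year is off by at most about 6 months (183 days).

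**The case against.** The strongest reply is that the documents do not show that any such dates exist. Protocol 6.5 requires start and stop dates for concomitant medications. Protocol 10.2 requires completed and source-supported CRF fields, and Protocol 10.4 provides for monitoring. Therapies and first opioid use are asked about every 3 months, so an event should be reported close to when it happened. Dates with a known month already have a workable rule. This stands: the number of affected events is unknown and may be zero. Follow-up by telephone after enzalutamide stops (Protocol Table 1, footnotes) makes incomplete dates plausible but does not show that they occur.

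A reader might infer three stronger things that the documents do not support.

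- **That the SAP sends year-only dates to the end of follow-up.** It does not say so. It says that they are not imputed, and never that a partial date counts as missing.
- **That the curves or the treatment comparison are biased.** This depends on how many dates are incomplete and in which arm. Nothing in the documents suggests a difference between arms, and with similar missingness the hazard ratio stays near 1.
- **That the last known study date must be the end of follow-up.** The term is undefined. The end of follow-up is its natural reading for a subject still in contact, and the delays above rest on it.

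The consequence is also limited. Next anticancer intervention and first opioid use are exploratory objectives (SAP 2.3), first chemotherapy is not a listed objective, the primary endpoint is not a time to event, and SAP 4 calls all analyses descriptive or exploratory. That lowers the severity. It does not make the rule right, since in a descriptive analysis the curves are the result.

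**Conclusion.** The point holds for fully missing dates of non-fatal events. The SAP states a rule, no other passage corrects it, and it can record an event up to about 2 to 3 years late, with the error in one direction only. This assumes that the last known study date means the latest contact and that contact continued well after the event. For year-only dates the same outcome is the more likely reading but remains an inference. What is certain there is that the two bullets are unreconciled. Any effect on estimates is conditional on such dates occurring: about 4 percentage points on an arm's event-free curve per relocated event, before censoring. The simulated shifts of about 4 to 10 points rest on assumed missing rates of 10% to 20% and say nothing about what happened in this trial. The stated power is unaffected. The rule is wrong as written, and the severity is low: a useful correction rather than a necessary one.

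**What to change.** Split the last bullet of SAP 3.4 in two and reconcile it with the partial-date bullet.

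- **Non-fatal event, incomplete date.** Use the midpoint between the last contact without the event and the first contact that reports it, bounded by any known month or year and by the randomization date. State that this covers both fully missing and year-only dates. Other bounded conventions, such as the first reporting contact or the middle of the known year, would also improve on the present rule. What matters is to fix one in advance.
- **Missing censoring date.** Keep the last known study date, and define it, for example as the latest documented visit or contact.

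Reporting the number of imputed event dates by arm for each endpoint would let readers judge whether the rule mattered.

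The cost is a sentence or two in the SAP and a short programming rule. No new data are needed, because the contact dates are already collected.
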